Lower limbs venous compression has been demonstrated to effectively decrease hypotension among women undergoing scheduled cesarean section (Cyna, Andrew, Emmett, Middleton, & Simmons, 2006; Goudie, Winter, & Ferguson,, 1988; Rout, Rocke, & Gouws, 1993; Sun et al., 2004; Van Bogaert, 1998). To date, only one study has examined the use of lower limbs venous compression to decrease hypotension in laboring women and found a significant reduction in maternal hypotension with the use of SCDs. This study compared women who used SCDs to a historical comparison group of women who received care before SCDs were provided and found a decrease in the incidence of maternal hypotension from 23.3% in the comparison group to 3.23% in the SCD group. and the researchers suggest a prospective randomized trial to investigate the phenomenon (Peyronnet et al., 2017). The purpose of this study is to build upon this preliminary work and to use a randomized controlled trial to examine the effectiveness of SCDs in preventing hypotension among a larger sample of laboring women who receive an epidural analgesia.

Research Plan

• Study Design

- This study will use a randomized, non-blinded, controlled design with two arms:
 - Arm 1: Patient will receive 1L of LR and have SCDs applied 15 minutes before epidural placement and will be removed 1 hour after epidural placement
 - Arm 2: Patient will receive 1L of LR during and after epidural placement with no use of SCDs

• Setting for the study

The study will take place on Bethesda North Hospital's Labor and Delivery Unit. This unit houses 12 labor rooms and provides care to approximately 10-12 laboring women each day.

• Participants

The study will enroll 120 women who meet the following inclusion/exclusion criteria:

Inclusion Criteria:

- \circ $\;$ Laboring at Bethesda North Hospital Labor & Delivery Unit
- Will receive epidural analgesia
- 37+ weeks gestation
- Singleton pregnancy
- Category 1 tracings only before epidural placement

Exclusion Criteria:

- Under 18 years old
- Does not speak English
- o Unable to consent to involvement in the research study
- Diagnosed with fetal demise
- Diagnosis of pre-existing hypertension
- Diagnosis of gestational hypertension

- Diagnosis of pre-eclampsia
- Diagnosis of diabetes
- Breech presentation
- Contraindications to lower leg compression (ex: fractured bones in leg, cellulitis, lower limb amputation, etc.)
- Contraindications to receiving 1L of LR

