- Blood pressure on admission SBP>160 or DBP>110
- Fetal heart rate abnormalities before epidural

Sample Size Determination: A power analysis was conducted using the primary outcome variable, maternal hypotension, with an expected difference similar to that found in the Peyronnet and colleagues' (2017) study (3.23% vs. 23.3%) (0.3), power of 0.8, and level of significance 0.05. It was determined that 44 patients would be needed in each group, for a total sample size of 88 patients. To allow us to also examine the impact on occurrence of infant Category 2 tracings and to allow for the possibility of removing participants from the final analysis due to missing data, we plan to enroll 120 patients (60 in each group).

• Data Collection

Before the study begins, information about the study will be provided to the providers. Providers who agree with involvement of their patients will be provided a hand-out about the study to give to their patients during prenatal visits and asked to mention to their patients that they may be approached about involvement of the study when they are admitted. The nurses on the L&D unit will be provided with education about the study purpose, exclusion criteria, and procedures. All nurses on the L&D unit have received training in the proper use of SCDs clinically. However, to validate and reinforce this knowledge, the nurses on the L&D unit will be provided education on proper measurement to determine boot size for SCDs and proper boot placement and SCD use. Nurses will be instructed to call a member of the study team immediately if any safety concerns occur related to the SCDs.

When a patient who meets the inclusion/exclusion criteria is admitted, a nurse will describe the study, answer any questions the patient has, and if the patient wants to enroll in the study, the study team nurse will review the information consent form. After the patient provides written informed consent, the nurse will remove the next envelope out of a box of prefilled and sealed opaque envelopes. The envelope will provide the Subject ID number to be used on all study-related documentation and the study Arm that the patient has been randomized to, either:

- 1. SCD Group + Fluid Bolus
- 2. Fluid Bolus Group (no SCD)

These envelopes will be filled using a computerized simple random number generator (1:1 randomization) prior to the start of the study.

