In addition to the group assignment, the envelope will include a data collection form. Data will be recorded directly on this form during the patient's visit. The form will collect the following information:

- \circ Whether patient was assigned to the SCD group or the standard care group
- Patient demographics including age, weight, and # pregnancies and # births
- Threshold systolic blood pressure (20% decrease from baseline) The study team nurse will calculate threshold systolic blood pressure by calculating the admission systolic blood pressure multiplied by 0.8
- \circ Biomed number of SCD machine (SCD group only)
- Leg measurement for SCD boot size determination (SCD group only)
- Size of boots placed (SCD group only)
- Biomed number of boots placed (SCD group only)
- Time SCDs placed on (SCD group only)
- o Time of epidural placement
- Whether patient received 1L of LR
- Time SCDs removed (SCD group only)
- Did the RN have to perform any interventions to address decreased fetal heart rate during the 1 hour after epidural placement? Yes/No
- Did the anesthesia provider treat the maternal blood pressure during the 1 hour after epidural placement? Yes/No
- All BPs and times of maternal blood pressures with SBP<90 or >20% decrease from baseline within the 1 hour after epidural placement

After delivery, the RN will complete the data collection form and place the signed informed consent form and data collection form in a locked room designated for study materials.

On the data collection forms, RNs are instructed to call a member of the study team immediately if there are any safety concerns related to the SCDs. If the study team receives a call about a safety concern, recruitment and enrollment of new participants will stop until the study team meets and reviews the incident and determines it is safe to continue. Any adverse events and serious adverse events will be reported to the IRB in compliance with IRB safety policies.

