Hypothesis 1: Laboring women who receive epidural analgesia and use SCDs will experience a lower incidence of hypotension compared to laboring women who receive epidural analgesia and do not use SCDs.

To compare the effects of the SCDs, a Chi Square test will be used to compare occurrence of maternal hypotension for patients who used SCDs to patients who did not use SCDs. A level of significance of α =0.05 will be used.

Hypothesis 2: Infants of laboring women who receive epidural analgesia and use SCDs will experience a lower incidence of Category 2 tracings compared to laboring women who receive epidural analgesia and do not use SCDs.

To compare the effects of the SCDs, a Chi Square test will be used to compare occurrence of Category 2 tracings of infants of patients who used SCDs to infants of patients who did not use SCDs. A level of significance of α =0.05 will be used.

Interim data analysis will occur (1) once approximately 1/3 of the participants have been enrolled in each group and (2) once approximately 2/3 of the participants have been

enrolled in each group. If interim calculations at time (1) or time (2) note a significant difference between groups in maternal hypotension or frequency of category 2 tracings, data collection will be completed at that time and final analysis will be completed.

Ethical Considerations

• Informed consent

All study staff will complete CITI training. A study staff member will meet with potentially eligible patients and describe the study and answer any questions. If the patient is interested and meets all the inclusion/exclusion criteria, the study staff will review the *Informed Consent Form* and obtain written informed consent. Patients will receive a copy of their signed Informed Consent form.

Informed Consent forms will be stored in a locked room that only staff will have access to. After the study closes, the signed Informed Consent forms will be boxed and sent to off-site storage and securely stored until the infant turns 21 years of age. At that time, the hard copy forms will be shredded.

• Privacy information

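### The primary chi-square test is valid but leaves admission SBP unused; prespecified adjustment for it is a cheap, modest improvement whose gain may be zero

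*Combined protocol and SAP*

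**What the plan says.** - **Primary test.** Under Statistical Analysis, Hypothesis 1: "a Chi Square test will be used to compare occurrence of maternal hypotension". No covariate, stratified analysis or supportive adjusted analysis is named, and no effect estimate or interval is specified.
- **Baseline SBP.** The form described under Data Collection carries a threshold: "The study team nurse will calculate threshold systolic blood pressure by calculating the admission systolic blood pressure multiplied by 0.8". Admission SBP is not itself listed, but it equals threshold/0.8.
- **Allocation.** "These envelopes will be filled using a computerized simple random number generator (1:1 randomization) prior to the start of the study". No blocks or strata are described.
- **Event definition.** The Hypothesis section counts an SBP below 90 mmHg or a fall of more than 20% from baseline. The Background section gives another definition, SBP below 90 or diastolic pressure below 60, in which baseline plays no part.
- **Size.** The planning rates come from a historical-comparison study that reported a "decrease in the incidence of maternal hypotension from 23.3% in the comparison group to 3.23% in the SCD group". From these, "It was determined that 44 patients would be needed in each group, for a total sample size of 88 patients". Enrolment is set at 120, 60 per arm.

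**The concern.** Under the Hypothesis 1 definition a woman has an event when her lowest SBP falls below the larger of 90 and 0.8 × admission SBP. Admission SBP is therefore built into the outcome for many women and is a natural candidate to predict it. The trial already has the value, yet neither randomisation nor analysis uses it.

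Two things are at stake. One is some power. The other is how the result reads if the arms happen to differ in admission SBP: without a prespecified adjusted analysis, any adjustment made after seeing the imbalance would carry little weight.

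**Working it through.** **1. The plan's own figure.** With p1 = 0.0323, p2 = 0.233, mean 0.13265, two-sided α = 0.05 (sidedness is not stated; two-sided without continuity correction reproduces the figure) and power 0.80:

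n = [1.96√(2 × 0.13265 × 0.86735) + 0.8416√(0.0323 × 0.9677 + 0.233 × 0.767)]² / 0.2007² = (0.940 + 0.386)² / 0.0403 = 43.6, so 44 per arm. The stated 44 reproduces. By the same approximation power is 80.3% at 44 per arm and 91.0% at 60. Expected events at 120 women: 60 × (0.0323 + 0.233) = 15.9.

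**2. Where admission SBP matters.** 0.8 × SBP exceeds 90 only when SBP > 90/0.8 = 112.5 mmHg. Below that the fixed 90 mmHg limb governs. With an assumed mean of 120, the share below 112.5 is Φ((112.5 − 120)/SD): 22.7%, 26.6% and 30.9% for SD 10, 12 and 15. High admission SBP raises the chance of a 20% fall and low admission SBP raises the chance of dropping below 90, so the relation can be U-shaped. With mean 122, SD 12 and correlation 0.6 between admission and lowest SBP, simulated control event rates were about 40% below 105 mmHg, 16% at 109 to 116 and 35% above 140, while the linear R² was 0.000.

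**3. Chance imbalance.** At 60 per arm the standardised difference in mean admission SBP has SD √(1/60 + 1/60) = 0.183. P(difference > 0.2 SD) = 27%; P(> 0.3 SD) = 10%.

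**4. Power with and without adjustment.** Assumptions, none from the documents: admission SBP mean 120, SD 10, 12 or 15; SD of lowest SBP 12; correlation 0.2 to 0.8. There were 6,000 trials per setting with simple randomisation. The Pearson chi-square is compared with the logistic score test for arm. Power (%) at 120 women, SD 12:

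| Rates | Correlation | Chi-square | Linear SBP | Linear + quadratic |
|---|---|---|---|---|
| 3.23% v 23.3% | 0.2 | 93.7 | 95.4 | 95.5 |
| | 0.4 | 93.8 | 94.2 | 94.4 |
| | 0.6 | 93.1 | 92.9 | 93.4 |
| | 0.8 | 93.7 | 96.1 | 96.9 |
| 12% v 23.3% | 0.2 | 37.2 | 39.7 | 40.2 |
| | 0.4 | 36.4 | 37.2 | 38.1 |
| | 0.6 | 36.8 | 36.8 | 38.1 |
| | 0.8 | 37.0 | 40.3 | 42.2 |

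Over all three SDs, the change with a linear term was −0.2 to 2.9 points at the planning rates and 0 to 5.4 at 12% v 23.3%. With the quadratic term it was 0.1 to 3.3 and 0.2 to 7.2. At 8% v 23.3% (mean 122, SD 12, 20,000 trials) a linear term took power from 64.6 to 70.4, 64.2 to 66.7 and 63.6 to 64.7 at correlations 0.2, 0.4 and 0.6. A repeat with 12,000 trials gave smaller changes: 65.4 to 69.9, 65.1 to 66.6 and 65.6 to 65.5. (Simulated chi-square power slightly exceeds the 91.0% of the approximation; the comparison is within simulation, so this does not matter.)

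**5. Size.** In the runs behind the table the chi-square rejected 4.9–5.5% under the null, the linear score test 4.6–5.6% and the quadratic 4.9–5.7%. The 12,000- and 20,000-trial runs put the linear test at 4.6–5.5% and 5.0–5.3%. A further 4,000-trial run ranged from 4.6 to 6.4%, against 4.9–5.6% for the chi-square. Size was checked at 120 women, not at the interim looks.

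**6. Size given imbalance.** Among null trials with an imbalance above 0.3 SD, at correlation 0.2 the chi-square rejected 9.3% (event rate 23.3%) and 7.6% (13.3%), against 5.0% and 4.7% after linear adjustment. At correlation 0.4 the figures were 6.1% and 7.0% against 4.0% and 5.0%. At 0.6 there was no meaningful difference.

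**7. An arm with no events.** At 3.23%, P(no SCD-arm events) = 0.9677⁶⁰ = 14%. At the interim looks, about 20 and 40 per arm, it is 0.9677²⁰ = 52% and 0.9677⁴⁰ = 27%. The score test survives, because it fits only the model without arm. The arm coefficient of the full model diverges, and the usual delta-method interval is then unusable.

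**The case against.** The strongest case against is that nothing here is an error. The chi-square under simple randomisation holds its 5% level averaged over randomisations, the stated sample size reproduces, and 120 women already give over 90% power at the planning rates. The benefit rests on assumed SBP values and can be nil. All of that stands, and it is why this is an optional improvement.

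Readers might infer three stronger things, none of which the documents support:

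- *That chance imbalance biases the planned test.* It does not; its error rate already allows for it. Step 6 concerns only the minority of trials with a marked imbalance.
- *That admission SBP sets the threshold for every woman, so it must predict the event and adjustment must gain power.* The 90 mmHg limb contradicts the first part, and the zero linear R² at correlation 0.6 contradicts the second.
- *That adjustment removes the effect of imbalance.* A single linear term corrects nothing where the relation is U-shaped. Adjustment reduces the effect at best.

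The objection does not answer the point that high power holds only at the very large planned difference, taken from a single historical-comparison study. At 8% v 23.3% chi-square power is about 65%, where a few points are worth having. The small number of events limits the model to one covariate; it does not rule that covariate out.

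**Conclusion.** The point holds as a modest, optional improvement. The planned test is valid but leaves unused a baseline value that the trial already has and that enters the Hypothesis 1 outcome above 112.5 mmHg. At 120 women, under the assumed SBP values, adjustment gains about 0 to 3 points of power at 3.23% v 23.3% and about 0 to 5 at weaker effects with a linear term (5.8 in the most favourable run; up to about 7 with curvature). There is no material loss and size stays near 5%. The gain may be zero, and the documents cannot settle where in the range it lies.

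The conclusion depends on the Hypothesis 1 definition. Under the Background definition baseline SBP does not enter the event, and the argument from construction falls away.

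**What to change.** 1. Prespecify as the primary test the logistic score test for assigned arm, with continuous admission SBP as the only covariate. Decide in advance whether to add a quadratic term, since the 90 mmHg limb can bend the relation. With about 16 expected events, add no other covariates.
2. Keep the chi-square as a sensitivity analysis.
3. Report a standardised risk difference with 95% CI from the logistic model. Prespecify the fallback when an arm has no events, for example the unadjusted risk difference with a score-type interval, and apply the same rule at the interim looks.
4. Record admission SBP itself on the data collection form beside the threshold.
5. State in the plan that adjustment reduces, and does not remove, the effect of chance imbalance, and that the gain may be zero.
6. Reconcile the two definitions of hypotension in the Hypothesis and Background sections before fixing the covariate.

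The cost is SAP wording, one field on the form and a short analysis program, with no extra patients or measurements. The documents do not show whether the named package, Intellectus Statistics, provides the score test and standardisation, so check this first. Confirm the size of the chosen model by simulation, including at the interim sizes, before finalising it.

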Weekly, the research specialist will collect the data collection forms. The research specialist will review the data collection forms and compile the medical record numbers for any patient who the RN marked "yes" to "Did the RN have to perform any interventions to address decreased fetal heart rate?" The research specialist will send two study team nurses the compiled list for the week to conduct a review of the medical records of the patients requiring interventions to address decreased fetal heart rate. The same two study team nurses will review all charts throughout the study and they will separately determine category of the fetal heart tracings and send them to the research specialist. The two study team nurses assigned to determine tracing categories will be blinded to which group the patient was in. The

research specialist will conduct interrater reliability each week and any discrepancies will be sent back to the two raters to review together and come to a consensus on category assignment.

• Intervention or experimental aspect of the study

Patients randomized to Arm 1 will have SCDs placed on their lower limbs 15 minutes before the epidural placement and they will be removed one hour after epidural placement. SCD use is in the Epic order set for laboring patients but is rarely used in practice on the unit. The SCD in clinical use at Bethesda North Hospital is the Kendall SCD Express Sleeves, knee length 700 series, Ref: 29525. In this study, the study team is using the device according to the indicated description "as the sleeves/cuffs compress the legs/feet, veins collapse, forcing the blood to move upward towards the heart" but not for the indicated outcome of "prevention of DVTs"; instead the study is testing the use of this device for a new indication – for prevention of maternal hypotension.

Patients randomized to Arm 2 will receive standard care.

• Statistical Analysis

Data recorded on paper data collection forms will be entered into a password protected database. Only study team members will have access to the database. No personal information will be entered into the electronic database. Data will undergo range checks when entered into the database, and quality control procedures will be performed to ensure accuracy of the data in the electronic database.

Statistical analyses will be performed using Intellectus Statistics statistical software. The following analyses will be performed to address each hypothesis:

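### Both chi-square tests group women by SCD use, and nothing says they are analysed in the arm to which they were randomised

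*Combined protocol and SAP*

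**What the plan says.** Under Statistical Analysis, the Hypothesis 1 test is to "compare occurrence of maternal hypotension for patients who used SCDs to patients who did not use SCDs". The Hypothesis 2 test compares Category 2 tracings in "infants of patients who used SCDs to infants of patients who did not use SCDs". The two hypotheses themselves are also worded by use. The interim rule stops data collection if the calculations "note a significant difference between groups in maternal hypotension or frequency of category 2 tracings", without saying how the groups are formed.

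Randomised assignment governs the envelopes and the form (Data Collection) and the delivery of care (Intervention or experimental aspect of the study). No section ties the analysis to it. There is no intention-to-treat statement, no named analysis population, and no rule for an Arm 1 woman who never has SCDs placed or an Arm 2 woman who does. The only ground given for removing a participant from the analysis is missing data (Sample Size Determination).

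The form does record "Whether patient was assigned to the SCD group or the standard care group". Its fields on actual SCD use are marked for the SCD group only.

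**The concern.** Randomisation makes the assigned arms comparable. It does not make women who used SCDs comparable with women who did not. If Arm 1 women who miss the device differ in their risk of hypotension, moving them to the control side confounds the primary result. The bias can favour SCDs or count against them. The same holds for Category 2 tracings.

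Some non-use is conceivable from the plan itself. Data Collection describes consent and opening of the envelope at admission, whereas SCDs go on 15 minutes before the epidural, so a woman could be randomised and not have them placed in time.

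The purpose of the trial makes this matter more. The Background justifies it as a randomised test of a result that came from a historical comparison group, and an analysis by use would bring back a non-randomised comparison.

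The by-use grouping also cannot be built reliably. The Intervention section notes that "SCD use is in the Epic order set for laboring patients but is rarely used in practice on the unit", so use in Arm 2 is possible, but the form has no field for it.

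**Working it through.** **Inputs from the protocol.** Hypotension risks of 3.23% with SCDs and 23.3% without, power 0.8, α 0.05, 44 per group required and 60 per group planned (Sample Size Determination). Interim looks at about 1/3 and 2/3 of enrolment (Statistical Analysis).

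**Assumptions.** All non-use rates and non-user risks below are assumed, because the documents give none. Use of SCDs in Arm 2 is set to zero.

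**The plan's own figure.** The two-sided pooled formula is n = [1.960·√(2p̄(1−p̄)) + 0.842·√(p₁(1−p₁) + p₂(1−p₂))]² / (p₁−p₂)², with p₁ = 0.233, p₂ = 0.0323 and p̄ = 0.13265. This gives (0.940 + 0.386)² / 0.2007² = 43.6, so 44 per group and 88 in total, as stated. The sample size is not in dispute.

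**False-positive rate, one final test.** Suppose SCDs have no effect and each randomised arm has 23.3% risk, with 60 per arm. Let k Arm 1 women never use SCDs and have risk r. To keep the Arm 1 average at 23.3%, the users' risk must be (60 × 0.233 − k·r)/(60 − k). Grouped by use, 60 − k users are compared with 60 + k others, whose average risk is (60 × 0.233 + k·r)/(60 + k). For example, with k = 12 and r = 0.45, users are at (13.98 − 5.40)/48 = 17.9% and the others at (13.98 + 5.40)/72 = 26.9%, a spurious gap of 9.0 points. Exact binomial enumeration of the uncorrected chi-square test at 0.05 gives:

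| Non-users of 60 | Their risk | Users' risk | Ratio | Rejection, by use | Rejection, as randomised |
|---|---|---|---|---|---|
| 1 | 45% | 22.9% | 1.96 | 5.1% | 5.2% |
| 2 | 45% | 22.6% | 2.00 | 5.3% | 5.1% |
| 3 (5%) | 45% | 22.2% | 2.03 | 5.9% | 5.1% |
| 6 (10%) | 35% | 22.0% | 1.59 | 5.9% | 5.1% |
| 12 (20%) | 23.3% | 23.3% | 1.00 | 5.2% | 5.2% |
| 12 (20%) | 35% | 20.4% | 1.72 | 9.5% | 5.1% |
| 12 (20%) | 45% | 17.9% | 2.52 | 21.0% | 4.8% |
| 12 (20%) | 15% | 25.4% | 0.59 | 7.5% | 5.1% |

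In the last row only 0.9 of the 7.5 points favour SCDs, so the bias can go against the device.

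**With the interim looks.** Simulation with looks at 20, 40 and 60 per arm, stopping at the first p < 0.05 on hypotension alone (400,000 replicates, non-users spread evenly):

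| Non-use / non-user risk | By use | As randomised |
|---|---|---|
| none | 11.0% | 11.0% |
| 5% / 45% | 12.0% | 10.8% |
| 10% / 35% | 11.8% | 10.9% |
| 20% / 35% | 15.5% | 10.8% |
| 20% / 45% | 27.7% | 10.2% |

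The 11% baseline comes from the unadjusted looks, which is a separate matter. Only the excess over the as-randomised column belongs to this point.

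**Power as randomised.** If a share f of Arm 1 are non-users at control risk, the Arm 1 risk becomes (1 − f) × 0.0323 + f × 0.233, which is 4.2%, 5.2% and 7.2% for f = 5%, 10% and 20%. At 60 per arm the normal approximation gives power of 91% (f = 0), 87% (5%), 82% (10%) and 69% (20%). Exact enumeration, which runs somewhat higher, gives as randomised versus by use: 94% vs 94% (f = 0), 84% vs 93% (10%) and 70% vs 93% (20%).

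No figure is given for Hypothesis 2, because the documents state no Category 2 rate.

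**The case against.** The strongest reply is that the wording is a label for the arms. Study Design defines the control arm that way ("Arm 2: Patient will receive 1L of LR during and after epidural placement with no use of SCDs"), and the envelope names the groups by SCD. The Background uses the same language for what it also calls the SCD group of the earlier study. Fixed group sizes of 60, interim looks by enrolment in each group, and raters blinded to group all fit assigned arms. Assignment is also the one grouping variable recorded for every woman, so it is the natural input to the test. This stands as evidence of likely intent. It does not supply the missing rule: the literal text still places an Arm 1 non-user with the controls, and nothing contradicts it. In an open-label trial with two interim looks, that choice should be fixed in advance.

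The second reply is that harm requires the literal reading, appreciable non-use and a different risk among non-users, and that the documents establish none of these. The intervention is short, in hospital and applied by trained nurses. This also stands. At 5% to 10% non-use the excess shown is about 1 percentage point, and the 21% and 28% figures need both 20% non-use and 2.5 times the users' risk.

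The third reply is that assigned-arm wording does not settle a woman randomised at admission who never has an epidural. That is true, but she has no outcome window under either grouping and falls under the plan's removal for missing data. It is not a reason to group by use.

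**Conclusion.** The concern holds. As written, both tests are defined by use and no statement ties the analysis to the randomised arm. Confidence is high on those two facts. It does not extend to the size of any bias, or to whether an analysis by use is really intended.

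The effect ranges from nothing (full adherence, or non-users at the same risk) through about 1 percentage point of extra false positives in the 5% and 10% non-use cases, to a 21% false-positive rate at a single final test in the most extreme case examined. All of these rest on assumed non-use rates and risks, no use in Arm 2, and a 23.3% control risk. The plan should be corrected, because the literal rule can turn a randomised comparison into a confounded one for both outcomes.

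**What to change.** Reword both tests and the interim comparisons along these lines: *compare participants randomised to Arm 1 with participants randomised to Arm 2, each analysed in the assigned arm whatever her SCD use*. Keep any comparison by use as supportive only, and report how many Arm 1 women had SCDs placed.

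This is a one-sentence change that needs no new data. If the arms were meant all along, it alters nothing but the text. The real cost is dilution: if non-users have control risk, exact power at 10% non-use is 84% as randomised against 93% by use. That gain by use depends on non-users being no different in risk, which the trial cannot guarantee. A supportive by-use comparison covering Arm 2 would need one extra field on the form. The change removes only the excess due to grouping by use and leaves the inflation from the unadjusted interim looks in place.

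### Category 2 tracings act as an unadjusted co-primary outcome: both hypotheses are tested at 0.05 with no order, and either one can end the trial, although only hypotension is named primary

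*Combined protocol and SAP*

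**What the plan says.** The protocol gives three different signals about how the two outcomes rank.

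- **Sample Size Determination** ranks them: "A power analysis was conducted using the primary outcome variable, maternal hypotension". The 44 per group comes from hypotension alone. Enrolment is then raised from 88 to 120 for two reasons, one being "To allow us to also examine the impact on occurrence of infant Category 2 tracings" and the other missing data. Category 2 tracings are not given a rate, an effect size or a power.
- **Hypothesis or Research Question** and **Statistical Analysis** set the two side by side as numbered, directional hypotheses. For Hypothesis 1, "a Chi Square test will be used to compare occurrence of maternal hypotension"; for Hypothesis 2, "a Chi Square test will be used to compare occurrence of Category 2 tracings of infants". Each is given a significance level of 0.05. No testing order, split of alpha or adjustment is stated, and Category 2 is nowhere called secondary, supportive or exploratory.
- **The interim paragraph of Statistical Analysis** weights them equally. The first look comes "once approximately 1/3 of the participants have been enrolled in each group" and the second at about two thirds. At either look, a "significant difference between groups in maternal hypotension or frequency of category 2 tracings" ends data collection and leads to the final analysis. No interim significance level is given.

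**The concern.** The label in the sample-size paragraph and the rule in the analysis section disagree. Under the interim rule, a result on Category 2 tracings can close the trial while hypotension, the outcome it was sized for, shows nothing. At the final analysis, no sentence says how a significant Category 2 result should be described if hypotension misses.

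The 5% level therefore belongs to each test separately. If the trial's conclusion can rest on either outcome, nothing in the plan holds the error of that conclusion at 5%. An early stop on Category 2 also has a direct cost: the primary question is left with about 20 or 40 women per arm instead of 60.

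**Working it through.** **1. The protocol's own figure.** Inputs from Sample Size Determination: 23.3% and 3.23%, alpha 0.05, power 0.80. The mean rate is (0.233 + 0.0323)/2 = 0.13265. With two-sided alpha, pooled variance under the null and no continuity correction:

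n = [1.960·√(2·0.13265·0.86735) + 0.842·√(0.233·0.767 + 0.0323·0.9677)]² / (0.233 − 0.0323)² = (0.940 + 0.386)² / 0.0403 ≈ 43.6, so 44 per group.

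The effect size of 0.3 gives the same: (1.960 + 0.842)²/0.3² = 87.2, so 88 in total. The stated size is reproduced. It assumes one outcome, one look and the whole 0.05.

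**2. Two tests at one final look, no SCD effect.** If the tests are independent, 1 − 0.95² = 9.75%; the upper bound is 0.05 + 0.05 = 10%. The Background describes a path from maternal pressure to the fetal tracing, so positive correlation is likely. The protocol gives no figure, so a range is assumed. From the bivariate normal distribution with limits ±1.96, and from simulated cumulative z-statistics at three equally spaced looks, each tested at 0.05:

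| Correlation | Either outcome, one look | Either outcome, three looks |
|---|---|---|
| 0 | 9.75% | 20.3% |
| 0.3 | 9.5% | 19.8% |
| 0.5 | 9.1% | 18.9% |
| 0.7 | 8.3% | 17.3% |
| 0.9 | 7.0% | not run |

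**3. The same with binary data.** Pearson chi-square tests were simulated at 60 per arm, with hypotension at 23.3% in both arms, Category 2 at 10-30% (assumed) and correlation 0-0.5. At one look, 9.3% to 10.2% of null trials were significant on at least one outcome. With hypotension as low as 13%, the lower end was 8.9%.

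**4. Benefit only.** Both hypotheses are directional, and a two-sided 0.05 test puts 2.5% on the side of benefit. For two independent tests at one look, 1 − 0.975² = 4.9%; at correlation 0.5 it is 4.5%. The comparator is 2.5% for hypotension alone, so the error still nearly doubles.

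**5. The looks as planned.** With looks at 20, 40 and 60 per arm, each at 0.05, the chi-square simulation gives about 11% for hypotension alone and 19% to 21% for either outcome. About 7-8% of null trials stop early on Category 2 alone.

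**6. What a fixed order costs.** Exact Pearson chi-square power for Hypothesis 1 at 23.3% against 3.23%, in a single test at 0.05, is 94% at 60 per arm, 87% at 44 per arm and 49% at 20 per arm.

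**The case against.** The strongest reply is that the protocol has already ranked its outcomes. It names one primary outcome and powers the trial on it, and the title, the purpose and the new indication being tested for the device all concern maternal hypotension. On that reading Hypothesis 2 is an ordinary secondary test, and an unadjusted secondary test does not raise the primary's error, which is 5% at a single look.

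Much of this stands. A reader might infer that the plan declares a positive trial whenever either test is significant at the final analysis, so that its final error is 10% where 5% was promised. The documents do not support that. No sentence defines a positive trial, none claims a 5% rate across both hypotheses, and the only either/or wording concerns when data collection ends. The 10% also counts differences in the direction of harm, and it describes a single-look design that this trial does not use.

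What the reply cannot explain is the interim rule. A purely secondary outcome would not be able to end the trial by itself, and nothing in the analysis section carries the primary label over to the tests. Nor does the directional count remove the problem, because the interim rule acts on any significant difference and the benefit-only error still nearly doubles.

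**Conclusion.** The point holds as a conflict between the named primary outcome and the testing and stopping rules. As run, Category 2 tracings are an unadjusted co-primary outcome. With no SCD effect, at least one significant difference is expected in about 9-10% of trials at a single final look (lower if the correlation exceeds about 0.5) and in about 17-21% with the three planned looks. Hypotension alone keeps 5% at one look but reaches about 11% over three.

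These figures assume looks at exactly one third, two thirds and full enrolment, each at two-sided 0.05. The protocol states neither the interim level nor the sidedness. Category 2 rates of 10-30% and correlations of 0 to 0.9 (0 to 0.7 for three looks) are assumptions. The unadjusted looks account for a large part of the error, so setting an order between the hypotheses is necessary but not sufficient.

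**What to change.** In Statistical Analysis, state that:

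1. Hypothesis 1 is the primary test, at two-sided 0.05 overall.
2. Hypothesis 2 is a confirmatory claim only if Hypothesis 1 is significant. Otherwise Category 2 tracings are reported as an estimate with a confidence interval and described as exploratory.
3. Significance on Category 2 tracings alone does not trigger the interim efficacy stop. Without this, the trial could end on a result that item 2 calls exploratory.
4. The interim looks at Hypothesis 1 use named, adjusted boundaries. Only then does the order hold overall error near 5%. If Hypothesis 1 crosses early, also state the level at which Hypothesis 2 is tested at that look.

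The cost is a few sentences and the choice of a boundary; no patients are added. The downside is that Category 2 cannot be claimed if Hypothesis 1 misses. At the protocol's own rates that should be uncommon: Hypothesis 1 power is about 94% at 60 per arm and about 87% if only 44 per arm can be analysed. Both figures are for a single test at 0.05, and adjusted boundaries would lower them somewhat, depending on the boundary chosen.
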